Angulus, LLC has developed a dual-component Angulus sensor to fill this gap in critical care technology. Angulus enables critical care practitioners to instantaneously understand a patient's elevation, identify when the patient is outside of the desired 30-45 degree recumbency scope, and efficiently correct the patient's orientation with immediate feedback. Angulus supports real-time minute-to-minute data display as well as longitudinal aggregation of data. It objectively measures a patient's elevation, provides alerts when patients are out of range, and allows users to query for instant data and aggregate trends. With Angulus, critical care teams can effortlessly view a patient's elevation angle at-a-glance, eliminating the need for burdensome and inexact HOB measurement tools. Further, the ability to collect real time continuous patient elevation data may provide the necessary longitudinal data to further refine and improve patient elevation guidelines.

We seek to empower critical care teams to increase adherence to the VAP-prevention bundle, and thereby improve patient outcomes in the intensive care unit. Enabling critical care treatment teams to view comprehensible on-demand data about a patient's real-time elevation will empower greater compliance to the VAP prevention practices, and thereby reduce the incidence of VAP and other VAEs.

To achieve our overarching goal, we will pursue the following four specific aims:

- 1. Conduct initial end-user focus groups with critical care teams and stakeholders at our evaluation site. In order to validate existing HOB-adherence pain points and determine which critical hardware and software features end-users find most essential, we will conduct focus groups with the critical care team at our evaluation site, Montefiore Medical Center.
- 2. Measure the effect of Angulus on patient-elevation (HOB) compliance. To validate the usefulness of Angulus in improving compliance with patient elevation, and to elucidate the usability and feasibility of Angulus, we will conduct a randomized crossover study implementing Angulus within two ICU's at our evaluation site, Montefiore. This study will allow us to determine the effect of the Angulus mechanism on compliance, and quantify the percentage of time patients are spending within the desired recumbency with Angulus, when compared to the current standard of care.

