Angulus will work collaboratively with our consortium-site PI, [name], at our evaluation site, Montefiore Medical Center, to implement a cluster randomized crossover trial of Angulus in human subjects.

The purpose of this trial is to determine how implementation of Angulus impacts compliance with patient elevation guidelines. *Our hypothesis is that real time feedback to nurses and bedside clinician from the Angulus sensor of the actual body angle of elevation of the patient rather than the angle of the bed can improve compliance to head elevation to 30 degrees in mechanically ventilated patients in the ICU.* In order to achieve this goal we will conduct a cluster randomized crossover study occurring in two (2) Intensive Care Units (ICU) at Montefiore Medical Center. Randomization will occur at the ICU level.

Study Population: To participate in this study a patient must meet all of the inclusion criteria and fail to meet any of the exclusion criteria.

[figure not shown]
The criteria for inclusion in this study are:

- Mechanical ventilation with any modality (e.g., endotracheal tube, tracheostomy)
- Age between 18 and 75 years

The criteria for exclusion from this study are:

- Patients with a known allergy to the encasing materials
- Patients who are advised to be positioned outside of the 30-45 degree scope.
- Patients with any major chest wall abnormalities, or defects, including but not limited to:
 - o post-cardiac surgical patients
 - o pectus excavatum (or any congenital chest wall deformity)
 - o complicated skin and soft tissue infections on the chest wall
 - o heart-lung machine systems

Study Design: This is a two arm, clustered randomized cross over trial looking to see whether feedback from the Angulus device will promote greater compliance to patient elevation in the ICU. The overall study design is see in Figure 4.

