After receiving full IRB approval, all ICU nurses will receive didactic training on VAP, the importance of head-of-bed elevation, and a refresher on best-practice guidelines for implementing and ensuring compliance with the VAP bundle. These trainings will take place on two (2) separate occasions before each period to ensure that all ICU nurses receive the training, and will incorporate an evaluation component to assess comprehension. During each period, research coordinator will screen each unit for newly intubated patients who fulfill the inclusion criteria but none of the exclusion criteria. Eligible patients in the study ICUs at all periods will be equipped with the Angulus Device by tape to their sternum. Each potential participant will be given a de-identified patient code. Subjects will be enrolled in the trial within 36 hours of intubation, and will remain in the trial until discharge from Note that the Angulus is placed externally on the patient's chest and secured with the ICU. adhesives similar to what is used for EKG leads used clinically in the ICU. Angulus' only function is to measure the angle of elevation of the patient in their current position. For further discussion on the protection of human subjects, please see the human subjects section. The Angulus device will be collecting data on patient elevation "in the background." This will allow us to quantify the extent to which compliance with patient elevation is compromised under existing workflow limitations.

During Period 1, each ICU will be randomized to Feedback of No Feedback. The ICU with feedback will be equipped with display device (ipod) corresponding to each Angulus device with an

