interactive software interface which displays the patient's elevation and sends a color-coded cue when patients fall outside of the desired patient elevation scope. Nurses will be able to set up the display device and utilize all of its functionality including a snooze feature, which allows providers to pause the cue when patients are having a procedure, which requires they be positioned outside of the desired recumbent scope (i.e. a chest x-ray, etc.), or if the device must be removed (i.e. for bathing). Having the Angulus sensor with the corresponding display device will allow nurses to intelligibly and efficiently understand a patient's elevation and make corrections as needed throughout their workday. Nurses can decide to use this information to reposition the patients to reach the target elevation. In ICUs that are randomized to NO Feedback in Period 1, the Angulus device not have a corresponding display device and the data on patient elevation will NOT be displayed to the nurses. Nurses will continue to operate under existing clinical practices for compliance with hospital practice for elevation > 30 degrees, checking patient elevation according to existing methods. In Period 2, each ICU will cross over to the other arm and in Period 3, they will cross over back to the original arm. Three ICU (Moses MICU, Moses SICU, Weiler MSICU) will be randomized as cluster with all patients who are mechanically ventilated in those ICU randomized as a cluster to Feedback or No Feedback. During all periods of the study, whether the bedside clinician/nurse decides to adjust the patient's body position or bed is left up to their clinical judgement.

Statistical Analysis:

The primary outcome is compliance to head of bed elevation to 30 degree or more. This will be measured as a continuous variable between 0% and 100% compliance. This is defined as: Compliance= 100 x ((Total time in minutes in which patients in ICU are elevated > 30 degree during period) / (Total time patients in ICU spent with Angulus device during period))

From an inferential point of view, our goal is to use the data collected by the Angulus sensor to evaluate the effect that real-time feedback mechanism has on improving compliance with patient elevation guidelines. Indeed, by automating the data collection pipeline, our study will gather patient levels with more ease and at a finer temporal scale than was previously possible. Secondary outcomes of interest include:

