- Frequency that patients in the ICU are rotated more than 30 degree within 24 hour days and association with development of decubitus ulcers. As the technology in Angulus measures movement in 3 dimensions, it automatically records rotation in addition to elevation of patients. Another best care measure for mechanically ventilated patients is regular turning of patients to prevent formation of decubitus ulcers. This analysis will explore whether frequency of rotation for a patient is associated with subsequent development of decubitus ulcers. In this analysis, patients from all period and ICUs will be combined but the analysis will be stratified by period and ICU.
- Frequency that patients in the ICU rotate more than 30 degree and have change in elevation of more than 15 degree within an hour and correlation with agitation as indicated by RASS.
 Frequent movement in patients on the ventilator can indicate agitation. RASS is a clinically collected parameter indicative of levels of consciousness and agitation.

Montefiore has 3 MICUs and all of the Montefiore ICU units has 12-16 beds. Based upon preliminary work, there are an average of 25 patients who are newly intubated each month within each ICU and the average duration of mechanical ventilation is 3 days. That translate to about 75 patient-vent days per month. Table 2 shows detectable difference given this expected sample size at different powers. We aim to conduct the study in 3 ICU over 3 months total.

Table 2. Sample Size needed based on the minimal detectable difference for mean time in range between the monitored group and the non-monitored group

	70%	75 %	80%	85%
--	-----	------	-----	-----

	Power	Power	Power	Power
Detectable Difference				
10% difference in means	80	94	100	120
15% difference in means	38	42	48	56
20% Difference in means	20	24	26	30
25% Difference in means	14	16	18	20

Aim 4: Integrate critical end-user functionality post-implementation with an agile and iterative product development approach and assess end-user satisfaction and usability scores.

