a. Human Subjects Involvement, Characteristics and Design

Angulus, as a product, has been developed specifically to improve compliance with patient elevation guidelines for ventilated patients in the ICU.

Aim 1 and 3 involves focus groups and surveys/questionaires of ICU care providers and hospital leaders in hospital safety and quality control who are often concerned about measuring, preventing and reporting VAP in the hospital. This will be conducted at Montefiore Medical Center and will involve anonymous participation from the respondents in which they will be queried about features and functionality of Angulus to help guide refinement of the product. No personal information or identifiers of the participants will be collected. We plan on a verbal consent from participants.

Aim 2 outlines a cluster cross over randomized clinical trial designed to evaluate the usefulness and feasibility of Angulus in a critical care setting. We will enroll ventilated patients from 3 ICUs in this trial. We anticipate that study participants will be older than 18, have an equal male to female ratio, and have poor health status. Randomization will occur at the unit-level, not the individual level, and each unit will serve as its

own control as with our current study design the assignments switch after each period. We will apply for a waiver of informed consent for data collection as this study fulfills all criteria for waiver of informed consent:

Subjects will be enrolled in the trial within 36 hours of intubation, and will remain in the trial until ICU discharge.

Participation is not limited by patients' race, sex, ethnicity or socioeconomic class, and no potential subjects will be excluded based on these criterion. We are not incorporating fetuses, neonates, pregnant women, children, prisoners or institutionalized individuals, although ventilated patients are considered to be a vulnerable population.

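### Table 2 sizes the trial for independent observations, but ICUs are randomised and analysed by period; the stated power does not hold at the listed N, and the number of ICUs is inconsistent

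*Combined protocol and SAP*

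**What the plan says.** **Unit of randomisation.** Approach, Aim 2: "Randomization will occur at the ICU level". Study Design: in Period 1 "each ICU will be randomized to Feedback of No Feedback", then crosses over in Period 2 and back in Period 3. Human Subjects Involvement, Characteristics and Design: "Randomization will occur at the unit-level, not the individual level".

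**Primary outcome.** The Statistical Analysis section defines compliance as 100 times a ratio. The numerator is "Total time in minutes in which patients in ICU are elevated > 30 degree during period"; the denominator is those patients' total device time in the same period. That is one pooled percentage per ICU per period.

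**Number of ICUs.** Specific Aims, aim 2: "we will conduct a randomized crossover study implementing Angulus within two ICU's at our evaluation site, Montefiore". The opening of Aim 2 in the Approach: "a cluster randomized crossover study occurring in two (2) Intensive Care Units (ICU) at Montefiore Medical Center". The Study Design text says otherwise: "Three ICU (Moses MICU, Moses SICU, Weiler MSICU) will be randomized as cluster". The sample-size paragraph and the Human Subjects section also say three.

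**Sample size.** The text expects 25 new intubations per ICU per month, in three ICUs over three months. It introduces Table 2 as the detectable difference at that expected sample. The table, captioned "Sample Size needed based on the minimal detectable difference for mean time in range between the monitored group and the non-monitored group", instead lists N for fixed differences of 10, 15, 20 and 25% at 70-85% power. The 80% column reads 100, 48, 26, 18. No SD, alpha, intracluster correlation, unit of N or primary analysis model is stated.

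**The concern.** A table for two independent groups does not describe a trial with two or three randomised units and six or nine outcome values. It has no term for ICU, for correlation within an ICU-period, for the crossover, or for the few degrees of freedom left after fitting them. N of 14 to 120 can only count patients or some other sub-unit, because that many ICU-period values never exist.

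This is the plan's only sample-size justification, and the Phase I Success Criteria turn on a 15% improvement. A reader would take the 15% row to mean that 48 gives 80% power. The expected accrual does not appear in the table, so it also fails to say what the planned trial can detect. The ICU count matters in its own right: with two ICUs, an ICU-period analysis that adjusts for period has one residual degree of freedom.

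**Working it through.** **1. Reproduce Table 2.** The inputs are not stated, so I solved for SD, assuming two-sided alpha 0.05 and 1:1 groups.

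Normal formula, N as total: N = 4·SD²·(1.960 + 0.842)²/d². At SD 18.2 and 80% power this gives 104.0, 46.2, 26.0 and 16.6 for d = 10, 15, 20, 25. Rounded up per arm, the totals are 104, 48, 26, 18, against the stated 100, 48, 26, 18. Over all 16 cells, 15 fall within a small rounding tolerance and 11 match exactly.

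Solving each cell with a two-sample t-test gives SD 17.0-18.4 (N total) or 24.8-26.3 (N per group). A one-sided test with N total gives 19.8-20.9. The unit of N and the sidedness therefore cannot be identified, but every fit is an independent-observation formula. I carry SD 18 (N total) and SD 25.6 (N per group) forward. Both return 0.81 for the 15-point, N = 48 cell under the independent t-test.

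**2. Set up the actual design.** Three ICUs, sequences F-N-F, F-N-F, N-F-N (F = feedback), nine ICU-period means of m patients each.

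- Sum of squares of the feedback indicator (SSX): 1.778 after ICU and period effects (3 residual df); 2.000 after ICU effects only (5 df).
- SE = √{[(1−ρ)·SD²/m + ρ·(1−c)·SD²] / SSX}, where ρ is the within-period ICC and c the between-period correlation (ratio of between-period to within-period ICC).
- Power from the non-central t.
- Assumed scenarios, none given in the documents: ρ = 0; ρ = 0.05 with c = 0.8; ρ = 0.05 with c = 0.5.

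**3. The listed N for 15 points at 80%.**

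- N = 48 total, SD 18, ρ = 0: m = 48/9 = 5.33 and SD²/m = 324/5.33 = 60.75. With period effects, SE = √(60.75/1.778) = 5.85, 15/5.85 = 2.57, critical t (3 df) = 3.18, power 0.42. With ICU effects only, SE = √(60.75/2) = 5.51, power 0.59.
- N = 48 per group (96 in all), SD 25.6, ρ = 0.05, c = 0.5, period effects: m = 10.67; variance = 0.95·655.36/10.67 + 0.05·0.5·655.36 = 58.4 + 16.4 = 74.8; SE = √(74.8/1.778) = 6.48; power 0.36.

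Ranges for the whole 80% column over the three scenarios:

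| Model | N total, SD 18 | N per group, SD 25.6 | Table 2 |
|---|---|---|---|
| ICU + period (3 df) | 0.34-0.45 | 0.29-0.44 | 0.80 |
| ICU only (5 df) | 0.48-0.62 | 0.41-0.61 | 0.80 |

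**4. Planned accrual.** 25 × 3 × 3 = 225 before exclusions, assuming one-month periods, so m = 25. Example at SD 18, ρ = 0, period effects: SE = √(324/25/1.778) = 2.70, power 0.94.

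| Quantity | SD 18 | SD 25.6 |
|---|---|---|
| Power for 15 points, period effects | 0.83-0.94 | 0.56-0.74 |
| 80% detectable difference, period effects | 11.5-14.4 | 16.3-20.5 |
| 80% detectable difference, ICU effects only | 8.9-11.2 | 12.7-16.0 |
| Same, Table 2's independent method (125 vs 100) | 6.8 | 9.7 |
| 80% detectable difference, period effects, if 15 per ICU-period remain (135 in all, assumed) | 14.8-17.1 | 21.1-24.3 |

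**5. Two ICUs.** Opposite sequences with period effects: SSX = 1.333, 1 df. Power for 15 points at 25 per ICU-period is 0.24-0.29 (SD 18) or 0.17-0.21 (SD 25.6).

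**6. Allocation.** If three ICUs were randomised independently, all would share a sequence with probability 2 × 0.5³ = 0.25. SSX after ICU and period effects is then 0, and feedback cannot be separated from period.

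**The case against.** **Correlation is not the main cause of the fall.** For N = 48 total at SD 18 with 3 df, power is 0.42 at ρ = 0 and 0.40 at ρ = 0.05, c = 0.5. Most of the loss comes from analysing nine means with 3 or 5 df. No model is stated, and a patient-level analysis is not excluded: at ρ = 0, adjusting for ICU with or without period, it gives 0.71-0.76. This stands as a qualification. The rough halving of power depends on the model. But the outcome as defined is an ICU-period value, and power stays below 0.80 in every model tried, including the patient-level one with no correlation at all.

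**The listed N are not the planned sample.** Nothing says the trial stops at 48, and 225 patients in three ICUs may well suffice. This also stands, and the point is confined accordingly. Whether 225 suffices depends on an SD and a unit of N that the plan omits.

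**Smaller points.** Table 2 does not say in a sentence that 14-120 suffice, although its caption presents them as the sizes needed. Accrual is also expressed in patient-ventilator days, so N might count days; the calculations treat it as patients. The method of randomising the ICUs is not specified, so the 0.25 is conditional on independent draws. None of these rescues the table.

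**Conclusion.** The point holds. Table 2 describes a different trial from the one planned. At its listed N of 48 for 15 points, power on ICU-period values is about 0.36-0.59 rather than 0.80. Across the 80% column it is 0.29-0.45 with period effects and 0.41-0.62 without. The table's own arithmetic is broadly sound; the method is wrong for the design. The conflict between two and three ICUs is a plain contradiction, and a material one: at 25 patients per ICU-period with period effects, power for 15 points is 0.56-0.94 with three ICUs and 0.17-0.29 with two.

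That Table 2 assumes independence is inferred from the fit and the absence of any clustering input; the document does not say so. The figures rest on two-sided 0.05, back-solved SDs, assumed correlations, a 2:1 split of sequences, and 15% read as percentage points. They treat the ICU-period value as an equal-weight patient mean. The defined ratio is time-weighted, and unequal monitored time is not included.

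The three-ICU trial is not shown to be underpowered. What is shown is that Table 2 cannot tell the sponsor what it can detect.

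**What to change.** 1. Reconcile the number of ICUs across Specific Aims (aim 2), the opening of Aim 2 in the Approach, Study Design, the sample-size paragraph and the Human Subjects section.
2. State the primary analysis: a model for ICU-period data with ICU effects, an explicit decision on period effects, and small-sample degrees of freedom.
3. Specify an allocation that cannot put every ICU in the same sequence.
4. Replace Table 2 with the detectable difference for that ICU-by-period design at the accrual expected after exclusions. State alpha and sidedness, the unit of N, the SD and its source, and a range of ICC and between-period correlation.
5. Withdraw the present entries (14-120) as sample sizes needed.

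The sponsor must supply the SD and the unit of N, so no single replacement figure is offered; the ranges above are illustrations.

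The cost is one recalculated table, one stated model, one allocation rule and one reconciled count, with no extra patients. The stated detectable difference will be less favourable than Table 2's method implies.
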